### 5.3.2. Analyses for Continuous Endpoints

Descriptive statistics [n, mean, standard deviation (SD), median, range (minimum, maximum)] will be provided.

## 5.4. Methods to Manage Missing Data

### 5.4.1. Imputation of Incomplete Dates

An incomplete date is any date for which either the day, month or year is unknown, but all three fields are not unknown. An incomplete date occurs when the exact date an event occurred or ended cannot be obtained from a participant.

Any partial dates will be displayed in data listings without imputation of missing days and/or months.

For many of the analyses, a complete date is necessary to determine if the event should be included in the analysis or to establish the duration of an event. In such cases, incomplete dates will be imputed as follows.

#### 5.4.1.1. Start Dates for Prior/Concomitant Medications

For prior/concomitant medications, the case report form permits the start date to have an unknown day and/or month.

- For missing start day only – Day will be imputed as the first day of the month (i.e., 1).
- For missing start day and month – Day and month will be imputed as the first day of the year (i.e., 1 January).

#### 5.4.1.2. Stop Dates for Prior/Concomitant Medications

- For missing stop day only – Day only will be imputed as the last day of the month (i.e., 28, 29, 30, or 31).
- For missing stop day and month – Day and month will be imputed as the last day of the year (i.e., 31 December).

#### 5.4.1.3. VOC start date (for purposes of summarizing parent study VOC history data)

- For missing start day only – Day will be imputed as the first day of the month (i.e., 1).
- For missing start day and month – Day and month will be imputed as the first day of the year (i.e., 1 January).

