### **3.4. Baseline Variables**

The following baseline variables will be summarized. No baseline variables will be used for statistical modeling.

- Demographics: age (years), sex, race, ethnicity, geographic region (North America, Sub-Saharan Africa).

Some of the following baseline data (unless mentioned otherwise) is not collected in C5351005 EDC and will be programmatically included from the parent study database and corresponding ADaM datasets:

- Baseline characteristics: weight (kg) (see Appendix 1.2), height (cm) and SCD genotype from the parent study.
- SCD history: HU use at parent study screening, L-glutamine use at parent study screening.
- VOC history

VOCs (meeting definition in Section 3.2.1) within 12 months of parent study screening visit will be summarized in the following manner:

- a) Total number of VOCs in the past 12 months prior to parent study screening visit across all participants, total participant years in the past 12 months prior to parent study screening visit, annualized incidence rate of VOC in the past 12 months prior to parent study screening visit.
- b) Number of VOCs in the past 12 months prior to parent study screening visit per participant.
- c) Number of participants experiencing at least one VOC of specified type in the 12 months prior to parent study screening visit.

The 12-month VOC summaries will be based on counting individual events over 365 days prior to parent study informed consent date (screening visit).

- SCD complications history from parent study includes (i) historical SCD complications (including episodes ongoing at parent study screening) and (ii) concurrent SCD complications (episodes ongoing at parent study screening).
- Medical History (coded using MedDRA) from parent study.

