## 5.2. Hypotheses and Decision Rules

No formal statistical hypothesis testing will be performed in C5351005 study. All statistical analyses will be used for estimation purposes only and as such no decision rules are required. All p-values will be considered descriptive in nature and will not be used for inference.

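### Setting partial VOC-history dates to the earliest possible day tends to undercount the descriptive VOC rate for the year before the parent study

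*SAP*

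**What the plan says.** SAP section 3.4 (Baseline Variables) lists VOC history among the baseline summaries, including the "annualized incidence rate of VOC in the past 12 months prior to parent study screening visit". It fixes the window: "The 12-month VOC summaries will be based on counting individual events over 365 days prior to parent study informed consent date (screening visit".

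SAP section 5.4.1 defines which dates are imputed: "An incomplete date is any date for which either the day, month or year is unknown, but all three fields are not unknown". It adds that imputation serves, among other things, to decide whether an event enters an analysis. Section 5.4.1.3, whose heading limits it to parent-study VOC history, then gives two rules. If only the day is missing, "Day will be imputed as the first day of the month (i.e., 1". If day and month are missing, "Day and month will be imputed as the first day of the year (i.e., 1 January".

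Two statements limit the reach of the table. Section 3.4 says "No baseline variables will be used for statistical modeling", and section 5.2 says "No formal statistical hypothesis testing will be performed in C5351005 study".

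**The concern.** The wording of 5.4.1.3 repeats the start-date rule for medications in 5.4.1.1. There it is paired with a latest-date rule for stop dates (5.4.1.2), so together the two widen the interval of use. A VOC in the history table is a point event that is either inside or outside a fixed look-back window. Moving its date earlier widens nothing. It can only carry a pre-consent event across the lower edge of the window and out of the count.

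At stake is a description of how severe the disease was before treatment. The study has no comparator (protocol section 5.2). SAP 6.2.1 reports an annualized on-treatment VOC incidence rate, and readers are likely to set it beside the annualized historical rate. The early-date rule applies to the history only, so nothing on the treatment side offsets it.

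**Working it through.** The documents state no historical VOC rate, no share of partial dates and no bias figure, so there is no figure of the plan's to reproduce. The check applies the rule to the calendar.

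**Inputs from the SAP.** The imputation rules of 5.4.1.3 and the 365-day window of 3.4.

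**Assumptions.** The window runs from consent minus 365 days to consent minus 1 day. Every day of 2022 is taken in turn as the consent date (2023 gives the same result). True event dates are spread evenly over days. Participant-years do not depend on event dates, so the rate changes in the same ratio as the count.

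**One worked case: consent on 15 June 2022, window 15 June 2021 to 14 June 2022.**
- Day and month missing, year 2021: imputed to 1 January 2021 and excluded. Yet 200 of the 365 window days (200/365 = 55%) lie in 2021.
- Day missing, June 2021: imputed to 1 June 2021 and excluded. Yet 16 of that month's 30 days lie inside the window.
- Day missing, September 2021: imputed to 1 September 2021 and correctly counted.
- Day and month missing, year 2022, event before consent: imputed to 1 January 2022 and correctly counted.

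**All consent dates, pre-consent events only.**

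| Date as recorded | In-window events dropped, mean | Range by consent date | Older events wrongly brought in |
|---|---|---|---|
| Complete | 0% | 0% | 0 |
| Day missing | 4.0% (14.72 of 365 days) | 0 to 8.2% | 0 |
| Day and month missing | 49.9% (182.0 of 365 days) | 0 to 99.7% | 0 |

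The year-only loss depends strongly on when consent falls: 292/365 = 80% for 15 March, 200/365 = 55% for 15 June and 108/365 = 30% for 15 September.

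**Effect on the rate.** Rate ratio = 1 − (share of events with that kind of partial date) × (share of those dropped).

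| Assumed share partial | Day missing | Day and month missing |
|---|---|---|
| 2% | 1 − 0.02 × 0.0403 = 0.999 | 1 − 0.02 × 0.499 = 0.990 |
| 5% | 0.998 | 0.975 |
| 10% | 0.996 | 0.950 |
| 20% | 0.992 | 0.900 |

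For mixtures:
- 10% day-missing and no year-only: 0.10 × 0.040 = 0.4% lost.
- 30% and 2%: 0.30 × 0.040 + 0.02 × 0.499 = 2.2%.
- 10% and 5%: 0.10 × 0.040 + 0.05 × 0.499 = 2.9%.
- 30% and 20%: 0.30 × 0.040 + 0.20 × 0.499 = 11.2%.

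The year-only share drives the larger figures.

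**Upper edge.** The window also ends at consent. With consent on 15 June 2022, a VOC on 20 June 2022 recorded only as June 2022 becomes 1 June 2022 and is counted, although it lies outside. If events up to 28 days after consent were on file:
- Day-missing dates: an average of 14.70 event-days come in against 14.72 going out, a net of about zero.
- Year-only dates: 27.8 come in against 182.0 going out, still a clear net undercount.

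**The case against.** A reader might infer that the history is always undercounted and can never be overcounted. The documents do not support that. Complete dates are unaffected, as are partial dates whose imputed day stays inside the window. For day-missing dates nothing is lost when consent falls on the 1st of a month (12 of 365 consent dates). The claim that overcounting is impossible needs a history file with no events on or after consent. SAP 3.4 describes VOCs before the screening visit, but does not say that the file is restricted to them.

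A reader might also take a total such as 3% to 11% as the size of the bias. That rests on assumed shares of partial dates. Section 5.4.1.1 says that the case report form allows an unknown day or month for medications; 5.4.1.3 says nothing of the kind for VOC history. A qualifying VOC needs a visit to a medical facility (SAP 3.2.1), so year-only dates for events in the past year should not be presumed common. If they are rare, the loss is small.

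The consequence is limited too. The table is descriptive, no baseline variable is modelled, and no before/after comparison of VOC rates is planned. An informal one would be weak anyway: everyone enrolled came through Part A (SAP 2.2.3), so 12 weeks of osivelotor (protocol section 3.1) lie between the history window and this study. Earliest-date imputation is also pre-specified and matches the SAP's convention for medication start dates.

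All of this narrows the point. It does not remove it: for pre-consent events the stated rule has a known direction of error, and the SAP has no count that would show how large it is.

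**Conclusion.** The concern holds as a tendency. For VOCs that precede consent, 5.4.1.3 can drop in-window events and cannot add older ones. The average loss is about 4% of in-window events lacking the day and about 50% of those lacking day and month, given consent and event dates spread evenly over the year. The historical rate therefore tends to be low, chiefly through year-only dates in the prior calendar year. The net size cannot be stated, because the documents do not give the number of partial dates or say whether events on or after consent are on file. If such events are on file, some would be wrongly counted, and for day-missing dates the two errors could roughly cancel.

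This is a minor point about a descriptive baseline table. It does not touch the on-treatment VOC rate, the negative binomial model or any safety endpoint.

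**What to change.** In SAP 5.4.1.3, replace the earliest-date rule with one midpoint rule: a partial VOC start date is imputed to the midpoint of the part of the known month or year that precedes the parent-study consent date. This should not be shortened to the 15th or 1 July, which is a different rule: for a year-only 2022 date with consent on 15 March 2022, the midpoint of the pre-consent part falls in early February, whereas 1 July lies after consent. Exclude events known to fall on or after consent.

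Report the number of partial dates by type. Add a sensitivity count of every pre-consent VOC whose partial date overlaps the 365-day window. For pre-consent events that count is an upper bound, and the present earliest-date count is a lower bound.

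Averaged over consent dates, the midpoint rule drops and wrongly admits about 12.5% each for year-only dates, and about 1% each for day-missing dates, relative to in-window events of that type. The net bias is then near zero, provided older VOCs are on file at a similar rate. If only VOCs from the past 12 months were recorded, the midpoint rule would still drop about 12.5% of year-only events, against 49.9% now.

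The cost is SAP wording and one derivation, with no new data. Some individual events will still be misclassified, in both directions, and the balance is not exact for any one consent date. With consent on 15 June 2022, year-only VOCs from 1 January to 14 June 2021 (165 days) would be wrongly admitted and none dropped. With consent on 15 September 2022, those from the 108 window days in 2021 would still be dropped and none admitted. The figure may also differ from the history rate reported in the parent study, which should be noted under the table. No endpoint analysis changes.

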#### 5.4.1.4. Start Dates for Adverse Events

For this study, there is no need for imputation of start dates of AE to define TEAE and to determine if the AE occurs prior to dosing based on the CRF design.

#### 5.4.1.5. Stop Dates for Adverse Events

AE stop dates will not be imputed.

#### 5.4.2. Imputation of AE data

If AE relationship is missing, relation status will be set to “Related”.

If AE severity is missing, severity will be imputed to “Severe” or the severity noted for the same AE during treatment period.

If AE seriousness is missing, no imputation of seriousness will be performed.

#### 5.4.3. Imputation of Laboratory data

This imputation will follow the CDISC Pfizer safety rulebook. Specifically,

- Data in the form of “>10” or “<10” will be converted to numeric values by adding or subtracting, respectively, a “fuzz” factor of 0.001 (for example, <10 will be converted to 9.999).
- Expressions of the form “>=” or “<=” will be converted to the end point (for example, “>=10” will be converted to 10).

#### 5.4.4. Pharmacokinetic Concentration Below the Limit of Quantification

In all data presentations (except listings), concentrations below the limit of quantification (BLQ) will be set to zero. In listings, BLQ values will be reported as “<LLQ”, where LLQ will be replaced with the value for the lower limit of quantification.

In summary tables, statistics will be presented for a particular dose arm when  $\geq 3$  evaluable measurements are available for a given timepoint and dose arm. Only minimum and maximum values will be presented when  $< 3$  evaluable measurements are available for a given timepoint and dose arm.

## 6. ANALYSES AND SUMMARIES

### 6.1 Primary Endpoint(s)

The safety estimand for the primary endpoints will consider all safety data collected. Specifically, all data collected on or after obtaining informed consent will be included in the analysis.

#### 6.1.1. Incidence of TEAEs

AEs will be mapped to system organ class (SOC) and preferred term using the Medical Dictionary for Regulatory Activities (MedDRA).

The following guidelines will be used to capture the different types of TEAEs based on the AE CRF:

- **Treatment-Related Adverse Events:** adverse events with relationship to study treatment (as recorded on the AE eCRF page, Relationship with study treatment = Related) reported by the investigator and those of unknown relationship (i.e., no answer to the question 'Relationship with study treatment').
- **Serious Adverse Events (SAE):** serious adverse events (as recorded on the AE eCRF page, Was the AE Serious = Yes).
- **Non-Serious Adverse Events:** non-serious adverse events (as recorded on the AE eCRF page, Was the AE Serious = No).
- **Adverse Events Leading to Interruption of Study Treatment:** adverse events leading to interruption of study treatment (as recorded on the AE eCRF page, Action taken with study treatment = Drug interrupted).
- **Adverse Events Leading to Dose Reduction:** adverse events leading to dose reduction (as recorded on the AE eCRF page, Action taken with study treatment = Dose Reduced).
- **Adverse Events Leading to Discontinuation of Study Treatment:** adverse events leading to discontinuation of study treatment (as recorded on the AE eCRF page, Action taken with study treatment = Drug Permanently Discontinued).
- **Adverse Events Leading to Death:** adverse event leading to death (as recorded on the AE eCRF page, Did the AE result in Death = Yes, as well as AEs of Grade 5).

TEAEs leading to study discontinuation will be derived based on the response to the following question in the AE CRF form: "Caused Study Discontinuation"

The overall incidence of TEAEs will be summarized (Section 5.3). This table includes: TEAEs (number of TEAEs and participants with TEAEs),

Number of participants with:

- TEAEs by maximum severity,
- Treatment-related TEAE,
- Treatment-related TEAE by maximum severity,
- Treatment emergent SAE,
- Treatment-related treatment emergent SAE,
- Treatment emergent non-serious AE,
- TEAEs leading to study discontinuation,
- TEAEs leading to study treatment discontinuation,

TEAEs leading to study treatment interruption,  
TEAEs leading to dose reduction,  
TEAEs leading to death.

The TEAEs will be summarized and tabulated at participant level using counts and percentages:

- TEAEs by SOC and PT
- TEAEs by SOC, PT and maximum reported severity
- Treatment-related TEAEs by SOC and PT
- Treatment emergent SAEs by SOC and PT
- Treatment-related treatment emergent SAEs by SOC and PT
- TEAEs leading to study discontinuation by SOC and PT
- TEAEs leading to study treatment discontinuation by SOC and PT
- TEAEs leading to study treatment interruption by SOC and PT
- TEAEs leading to dose reduction by SOC and PT
- TEAEs leading to death by SOC and PT
- Treatment emergent non-serious AEs by SOC and PT

AEs will be sorted in alphabetical order for SOC and then overall descending frequency of PTs within each SOC by all participants.

The frequency of participants who experience each TEAE or treatment-related AE will be determined as follows: A participant experiencing the same AE multiple times will only be counted once for the preferred term. Similarly, if a participant experiences multiple AEs within the same SOC, that participant will be counted only once for that system. If changes in the severity of an AE are recorded in the eCRF, only the most severe incidence of the AE will be counted. If a participant experiences multiple occurrences of a TEAE, only the most severe related event or the worst severity (analysis dependent), will be counted for each participant within each SOC or preferred term for the summaries of treatment-related AEs.

Listing of all AEs will be provided.

A separate listing of deaths, if any, will be provided.

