#### **9.4.12. Disease-related Events or Disease-related Outcomes Not Qualifying as AEs or SAEs**

##### **9.4.12.1. Adverse Events that are Vaso-Occlusive Crisis Events**

VOC events are not reported as an AE/SAE and must be reported on the VOC page.

If the underlying cause of an SAE is determined to be a VOC, then the SAE will be entered on the VOC page and not reported as an SAE.

If the underlying cause of an SAE is determined not to be a VOC, then the SAE must be recorded in the SAE page and reported as an SAE.

The following disease-related events are common in participants with SCD, independent of exposure to study intervention, can be serious/life-threatening, and are defined as endpoints in this protocol:

- Uncomplicated VOC (defined as an acute episode of pain with no medically determined cause other than a vaso-occlusive event, results in a visit to a medical facility (hospitalization, emergency department, urgent care center, outpatient clinic, or infusion center), and requires parenteral narcotic agents, parenteral nonsteroidal anti-inflammatory drugs (NSAIDs), or an increase in treatment with oral narcotics, but is NOT classified as an acute chest syndrome, hepatic sequestration, splenic sequestration, dactylitis, or priapism.)
- Complicated VOC:
  - Acute chest syndrome
  - Hepatic sequestration
  - Splenic sequestration
  - Priapism requiring a visit to a medical facility
  - Dactylitis

Because these events are typically associated with the disease under study, they will not be reported according to the standard process for expedited reporting of SAEs even though the event may meet the definition of an SAE. These events will be recorded on the VOC page in the participant's CRF within 72 hours. These disease-related events will be monitored by an independent data monitoring committee and safety review team on a routine basis.

Note: However, if either of the following conditions applies, then the event must be recorded and reported as an SAE (instead of disease-related events):

- The event is, in the investigator's opinion, of greater intensity, frequency, or duration than expected for the individual participant.

OR

- The investigator considers that there is a reasonable possibility that the event was related to study intervention.

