#### **9.4.12.1.1. Procedures for Reporting and Documenting VOC Event Data**

All VOCs, as defined in Section 9.4.12.1, are to be documented within the eCRF within 5 days of a site becoming aware of such event. Each VOC is to be recorded only once on the "Vaso-Occlusive Event" eCRF page. All VOCs are to be recorded throughout the entire treatment period, up to Week 48, and should continue until the Follow-Up Visit at Week 60 for participants who do not enroll in the OLE study (or earlier if participant discontinues from the study). The Investigator will classify and provide all the following information for each VOC as follows:

- Diagnosis, which will be limited to one of the pre-defined VOC events as described in Section 9.4.12.1:
  - Uncomplicated VOCs
  - Acute chest syndrome
  - Hepatic sequestration
  - Splenic sequestration
  - Priapism (requiring a visit to a medical facility)
  - Dactylitis
- Onset date,
- Stop date,
- Action taken (none, required concomitant medication, temporarily withheld study drug, permanent discontinuation of study drug, or other [explain]),
- Whether or not hospitalization or a visit to emergency department, urgent care center, outpatient clinic, or infusion center was required,
- Concomitant medications given, and
- Outcome (recovered without sequelae, resolved with sequelae, ongoing, unknown, death).

If a participant is hospitalized due to a VOC and during hospitalization develops a non-VOC event that meets the criteria for a SAE, then that event should be reported as a SAE. Any prolongation of a hospitalization due to a non-VOC event (even though they may have initially been hospitalized due to a VOC) is reportable as a SAE in the eCRF.

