#### **9.4.12.1.2. Source Document Collection for VOC Event Adjudication**

For each reported VOC, blinded source documentation to support the reported diagnosis will be submitted by the site to the VOC adjudication committee. Adjudication of all potential VOC events reported by the Investigator will be performed by a study Adjudication Committee – an independent, blinded panel comprised of experts in SCD. Responsibilities of the Adjudication Committee and definition of VOCs for adjudication will be provided in the Adjudication Committee Charter.

Source documents may include (but are not limited to) the following:

- Clinical notes (including history and physical examination [PE] findings),
- Emergency Department notes (including history and PE findings),
- Hospital discharge summary,

- Clinical laboratory values (eg, Hb concentration values for diagnoses of hepatic or splenic sequestration),
- Physical examination findings,
- Concomitant medications, and
- Chest X-ray (required for reporting an ACS).

Endpoints will be adjudicated by an independent endpoint adjudication committee. Any SAE that is adjudicated by the endpoint adjudication committee NOT to meet endpoint criteria is reported back to the investigator site of incidence. The investigator must report the SAE to Pfizer Safety within 24 hours of being made aware that the SAE did not meet endpoint criteria. The investigator's SAE awareness date is the date on which the investigator site of incidence receives the SAE back from the endpoint adjudication committee.

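### Deaths, serious events and drug holds caused by a VOC can be absent from every planned safety summary table, and VOC-driven stops from all but disposition, because SAP 6.1.1 reads only the AE page

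*SAP*

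**What the plan says.** **Recording.** Protocol 9.4.12.1 sets the default: "VOC events are not reported as an AE/SAE and must be reported on the VOC page". If a VOC turns out to be the cause of an SAE, "then the SAE will be entered on the VOC page and not reported as an SAE". Two exceptions send a VOC to SAE reporting. One is that the investigator thinks it "of greater intensity, frequency, or duration than expected for the individual participant". The other reads "The investigator considers that there is a reasonable possibility that the event was related to study intervention".

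Protocol 9.4.12.1.1 lists what the VOC page holds. The choices for action taken include "temporarily withheld study drug, permanent discontinuation of study drug". The outcome entry reads "Outcome (recovered without sequelae, resolved with sequelae, ongoing, unknown, death". The page also records whether hospitalisation or another facility visit was needed. Under Protocol 9.4.12.1.2, "Any SAE that is adjudicated by the endpoint adjudication committee NOT to meet endpoint criteria is reported back to the investigator site of incidence".

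**Analysis.** SAP 6.1.1 defines an AE leading to death as "as recorded on the AE eCRF page, Did the AE result in Death = Yes", and adds AEs of Grade 5. SAEs and AEs leading to permanent discontinuation, interruption or dose reduction are likewise defined from AE eCRF fields. Study discontinuation comes from a question on the same form. SAP 6.2.1 gives VOC totals, counts per participant, annualised rates and a listing. SAP 6.5.2 plans a disposition table of participants who stop treatment or study, with the primary reason. SAP 6.1 says that the primary safety estimand takes in all of the safety data gathered.

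**The concern.** The protocol moves a class of events off the AE page, together with their fatal outcomes and drug actions. The SAP then builds its tables of serious and consequential events from the AE page and does not bring the moved information back. SAP 2.1, which lists departures from the protocol's analysis, does not mention this.

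Long-term safety is the primary objective. The events at issue, such as a fatal acute chest syndrome or a crisis after which drug was stopped or held, are among the most important that this study can observe. A reader who takes the 6.1.1 tables as the account of mortality, serious events and stopping could see fewer than occurred, with no table showing the remainder.

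**Working it through.** The plan gives no figure to reproduce and tests no hypothesis, so the check traces events through the planned outputs.

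**Step 1. Follow an event that stays on the VOC page.**

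| Event on VOC page only | TEAE tables (SAP 6.1.1) | VOC summary (SAP 6.2.1) | Disposition (SAP 6.5.2) |
|---|---|---|---|
| Death | Not included | Counted as a VOC if on treatment, not as a death | May appear as a study discontinuation; reason categories are not given |
| Serious VOC | Not included | Counted as a VOC; no split by hospitalisation | Not covered |
| Permanent stop | Not included | Counted as a VOC only | Counted, with primary reason |
| Temporary hold | Not included | Counted as a VOC only | Not covered |

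Two listings remain. The VOC listing in 6.2.1 could show these events one by one. The deaths listing in 6.1.1 states no data source, so it cannot be said whether VOC deaths are in it.

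**Step 2. Test the routes back to the AE page.** Both exceptions in Protocol 9.4.12.1 rest on the investigator's opinion. Neither is triggered by a fatal outcome or by a change to study drug as such. Adjudication returns only SAEs found *not* to meet the endpoint criteria, so a confirmed VOC stays on the VOC page.

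**Step 3. Compare the time windows.** The TEAE window in SAP 3.1.1 runs from first dose to last dose plus 56 days. The VOC summary is on-treatment, with participant-years = (EOT date − first dose date + 1)/365.25, and SAP 5.1 takes the EOT date as the last dose. A VOC in the 56 days after the last dose that is kept on the VOC page can therefore fall outside both summaries.

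**Step 4. Check the related endpoint.** The SCD-related AE endpoint (SAP 3.2.3 and 6.2.3) is also limited to AEs. Six of its ten preferred terms are VOC types: crisis, acute chest syndrome, hepatic sequestration, splenic sequestration, priapism and dactylitis. It can pick up only those that reached the AE page.

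**Step 5. Size.** For a given outcome (deaths, say), let v be the share caused by a VOC and e the fraction of those also reported as AEs. Then

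share missed by the 6.1.1 table = v × (1 − e).

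At e = 1 this is v × 0 = 0; at e = 0 it is v. The documents give neither quantity. To show only how the formula behaves, assume v between 10% and 50%. The missed share is then 10% to 50% at e = 0 (0.10 × 1 and 0.50 × 1) and 0% at e = 1. This is not an estimate for the study.

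**The case against.** The strongest reply is that much of this is by design. Protocol 9.4.12 treats VOCs as disease-related endpoints that do not qualify as AEs, so a table labelled as TEAEs leading to death is correctly labelled when it omits one. That stands. A reader might infer that the TEAE tables are wrong and should absorb VOCs; the protocol decided otherwise, and the point does not ask for it. What the reply leaves open is that no other planned table picks up the deaths, serious outcomes and holds moved elsewhere.

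A reader might also infer that every discontinuation summary is AE-based. It is not: the disposition table counts all treatment stops with a primary reason. It does not cover holds or serious events.

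A fatal crisis may well be judged worse than expected and so be reported as an SAE. The VOC-type terms in the SCD-related AE list also suggest that the SAP expects some of these events in the AE data. Both facts make e greater than zero plausible. They do not guarantee capture, because similar events could be classified differently at different sites.

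Finally, the CRF itself is not available here. The recording period in Protocol 9.4.12.1.1 (Week 48, then Week 60 for those not entering the OLE) appears to be carried over from the parent study. Whether the listed fields exist in this study's eCRF, and how long after the last dose they are filled in, needs confirmation.

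**Conclusion.** The gap is real and worth closing, but it is a possibility of omission, not a demonstrated undercount. VOC deaths, serious VOCs and VOC-driven holds can be absent from all planned safety summary tables. VOC-driven stops can be absent from all but disposition. This sits poorly with an estimand said to cover all safety data.

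The share missing from the 6.1.1 tables lies between zero and v. The documents support no narrower statement, so a claim that deaths will be understated by some stated percentage would have no basis. Nor can it be said that the deaths listing will disagree with the table: with no stated source it might match or might differ.

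The conclusion assumes that sites follow Protocol 9.4.12.1 as written and that the VOC page carries the fields in 9.4.12.1.1.

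**What to change.** Keep the TEAE tables as defined and leave the clinical and reporting rules unchanged. In the SAP:

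- Add to 6.1.1 one all-source table of deaths, permanent discontinuations and interruptions. Draw it from the AE page and the VOC page, plus the EOT and EOS pages for deaths and stops. Use the TEAE window (to last dose plus 56 days), show each source in its own row, and count a participant once in each total.
- Add a table of VOCs by outcome, hospitalisation and action taken, so that serious VOCs are visible without being relabelled as SAEs.
- State that the deaths listing uses all sources.

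The cost is SAP wording and one or two extra tables. Before committing, confirm that the eCRF holds the fields in Protocol 9.4.12.1.1, that hospitalisation can be separated from other facility visits, and that VOC recording continues through the 56 days after the last dose. If those checks pass, no new data are needed.
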